4.3.2.2. The Analysis Related to the Efficacy Estimand

The analysis related to the efficacy estimand will be conducted utilizing data in the EAS.

For the mean percentage of body weight change from randomization, an MMRM will be conducted. Restricted maximum likelihood (REML) will be used to obtain model parameter estimates, and the Kenward-Roger option will be used to estimate the denominator degrees of freedom. The response variable of MMRM will be the percent change in body weight from baseline values obtained at each scheduled postbaseline visit.

For the percentage of participants achieving at least 5% body weight reduction from randomization to the 72 weeks visit, a logistic regression model will be used with the response variable of the percentage of participants achieving at least 5% body weight reduction (Yes or No), with the missing value imputed using the predicted value from MMRM analysis followed by dichotomization. The terms for the logistic regression model will be the same as those for the treatment regimen estimand.

For the MMRM model, the independent variables of analysis model are treatment group, visit, and treatment-by-visit interaction; stratification factors (country and sex) as fixed effects; and baseline body weight as a covariate. An unstructured covariance structure will model the relationship of within-patient errors. If this model fails to converge, the following variance-covariance structures will be tested in order until convergence is achieved:

- heterogeneous Toeplitz
- heterogeneous first order autoregressive
- heterogeneous compound symmetry
- Toeplitz
- first order autoregressive, and
- compound symmetry.

The first covariance structure that converges will be used.

With the aid of the MMRM analysis, the 2-sided 95% CI for mean percent change in body weight from randomization to the 72 weeks visit for tirzepatide MTD compared to placebo will be derived and summarized. The resulting least-squares-mean estimates of mean percent change in body weight from baseline will be plotted by visit and by study treatment.

With the aid of the logistic regression model, the 2-sided 95% CI and odds ratio for percentage of participants achieving at least 5% body weight reduction from randomization to the 72-week visit for tirzepatide MTD compared to placebo will be summarized.

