Since the mean percent change in body weight and proportion of participants with  $\geq 5\%$  body weight reduction needs to be achieved at the same time, no multiplicity adjustment is planned for these 2 tests.

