- Treatment condition of interest - Tirzepatide MTD versus placebo, excluding data after discontinuation of study drug.
- Handling of ICEs - The ICEs leading to treatment discontinuation for any reason are addressed by the treatment condition of interest attribute and handled by the hypothetical strategy as described in the ICH E9 (R1) Addendum.
- Population-level summary - Difference in mean changes between treatment conditions AND difference in response percentage between treatment conditions as assessed by odds ratio.

Rationale for Estimand

The estimand aims to reflect treatment efficacy in an envisaged scenario in which the ICEs leading to treatment discontinuation would not occur.

This estimand is referred to as the “efficacy” estimand in the latter sections.

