2.1. Multiplicity Adjustment

For primary and key secondary efficacy objectives, the details of type I error control strategy are illustrated in [Figure GPHM.2.1](#). Both efficacy estimand and treatment regimen estimand will be used to assess those objectives. As they are intended for different purposes, no multiplicity adjustments will be made for conducting separate analyses relative to the efficacy and treatment regimen estimands. In addition, no multiplicity adjustments will be made for evaluating other secondary and exploratory objectives and safety assessments.

Abbreviation: H = hypothesis.

Figure GPHM.2.1. Type 1 error control strategy for primary and key secondary efficacy endpoints.

3. Analysis Sets

For purposes of analysis, the following populations are defined.

Table GPHM.3.1. Description of Analysis Datasets

Population	Description
Entered	All participants who sign informed consent
Enrolled	All participants who are enrolled in the 12-week lead-in period
Randomized	All participants who are randomly assigned a study drug
Modified Intent-to-Treat (mITT)	All randomly assigned participants who are exposed to at least 1 dose of study drug. Participants will be included in the treatment group to which they were randomized.
Efficacy Analysis Set (EAS)	Data obtained during the double-blind treatment period from the mITT population, excluding data after discontinuation of study drug (last dose date + 7 days)
Full Analysis Set (FAS)	Data obtained during the treatment period from the mITT population, regardless of adherence to study drug
Safety Analysis Set (SS)	Data obtained during the treatment plus follow-up period from the mITT population, regardless of adherence to study drug

Note: Unless otherwise specified, for analyses guided by the treatment regimen estimand, the FAS will be used. For analyses guided by the efficacy estimand, the EAS will be used, and for safety analysis, the SS will be used.

4. Statistical Analyses

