4.3.2. Main Analytical Approach

4.3.2.1. The Analysis Related to the Treatment Regimen Estimand

The analysis related to treatment regimen estimand will be conducted using data in the FAS.

The analysis for the mean percent change in body weight will be conducted utilizing ANCOVA. The response variable for the ANCOVA model will be percent change in body weight from randomization at 72 weeks. A logistic regression model will be used for the analysis of the percentage of participants achieving at least 5% body weight reduction obtained at the 72-week visit. Both models will include terms of treatment group, country/pooled country, and sex as fixed effects and baseline body weight as a covariate. The ANCOVA analysis will be conducted with hybrid imputation of missing body weight at 72 weeks (see Section 4.3.2.3 for details) and statistical inference over multiple imputation of missing data guided by Rubin (1987). For the

logistic regression, missing body weight data at 72 weeks will be imputed first, based on Section 4.3.2.3, then the continuous measurements will be categorized into status of achieving at least 5% body weight reduction (Yes or No).

With the aid of the ANCOVA model, the 2-sided 95% CI for mean change in percentage of body weight from baseline to the Week 72 visit between tirzepatide MTD and placebo will be derived.

With the aid of the logistic regression model, the 2-sided 95% CI and odds ratio for percentage of participants achieving at least 5% body weight reduction from baseline to the Week 72 visit between tirzepatide MTD and placebo will be derived.

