4.4. Secondary Endpoint(s) Analysis

4.4.1. Key Secondary Analyses Subject to Type 1 Error Rate Control

Table GPHM.4.2. Secondary Measures Controlled for Type 1 Error

Objectives	Relative to the Efficacy Measure	Analysis Conducted in a Manner Similar to	Additional Information
Tirzepatide MTD QW is superior to placebo from randomization for maintaining body weight reduction achieved during the 12-week lead-in period (measured at 72 weeks)	Percentage of study participants who maintain $\geq 80\%$ of the body weight lost during the 12-week lead-in period	Logistic model in Section 4.3.2.1 for treatment regimen estimand and logistic model in Section 4.3.2.2 for efficacy estimand	
Tirzepatide MTD QW is superior to placebo from randomization for body weight reduction (measured at 72 weeks)	Percentage of participants achieving body weight reduction $\geq 10\%$, $\geq 15\%$, and $\geq 20\%$ from randomization at 72 weeks	Logistic model in Section 4.3.2.1 for treatment regimen estimand and logistic model in Section 4.3.2.2 for efficacy estimand	
Tirzepatide MTD QW is superior to placebo from randomization for waist circumference reduction (measured at 72 weeks)	Mean change in waist circumference (cm) from randomization at 72 weeks	ANCOVA model in Section 4.3.2.1 for treatment regimen estimand and MMRM model in Section 4.3.2.2 for efficacy estimand	LSM estimates will be plotted by treatment through 72-weeks.

Abbreviations: ANCOVA = analysis of covariance; LSM = least squares mean; MMRM = mixed model for repeated measures; MTD = maximum tolerated dose; QW = once weekly.

Decision will be guided by the 2-sided p-values in each objective, and details will be included in Section 2.1.

For submission of Study GPHM to the US FDA to support the registration of tirzepatide for chronic weight management, the key secondary efficacy assessment will be guided by the treatment regimen estimand, conducted using the same population as the primary analysis. Assessment of the key secondary objective will be conducted with hybrid imputation of missing data (see Section 4.3.2.3).

For other regulatory agencies, publications, and other purposes, the assessment of key secondary efficacy objectives may be guided by the efficacy estimand, using the same population as the primary analysis.

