4.5. Exploratory Endpoints Analysis

Table GPHM.4.4. Exploratory Efficacy Analysis

Objective	Relative to the Efficacy Measure	Analysis Conducted
Compare tirzepatide MTD QW with placebo for body weight reduction at 72 weeks	Percentage of participants achieving $\geq 25\%$ body weight reduction from randomization at 72 weeks	Logistic model in Section 4.3.2.2
Compare tirzepatide MTD QW with placebo for body weight reduction at 72 weeks	Percentage of participants achieving $\geq 10\%$, 15%, 20%, and 25% body weight reduction from Week -12 at 72 weeks	Logistic model in Section 4.3.2.2
Assess changes in BMI from Week -12 at Week 0	Percentage of participants whose BMI shifts between clinically relevant categories, that is, from Week -12 (<25, 25 to <30, 30 to <35, 35 to <40, ≥ 40) to Week 0 (<25, 25 to <30, 30 to <35, 35 to <40, ≥ 40)	Shift analysis will be conducted based on data from enrolled participants.
Compare tirzepatide MTD QW with placebo for BMI shifts from Week 0 at 72 weeks	Percentage of participants whose BMI shifts between clinically relevant categories, that is, from Week 0 (<25, 25 to <30, 30 to <35, 35 to <40, ≥ 40) to 72 weeks (<25, 25 to <30, 30 to <35, 35 to <40, ≥ 40)	Shift analysis will be conducted based on data from the EAS.
Visualize tirzepatide MTD QW and placebo percentage of body weight reduction, from Week -12 up to the safety follow-up after 72 weeks	Percentage of body weight reduction from Week -12 to 72 weeks plus 4 weeks safety follow-up	Time-course plot will be generated. Only the participants who complete the 72 weeks of treatment and have the safety follow-up visit (Visit 801) will be included.
Assess changes from Week -12 at Week 0 and compare tirzepatide MTD QW with placebo in parameters from Week -12 at 72 weeks	Mean change in 
 • systolic blood pressure • diastolic blood pressure • total cholesterol • HDL-C • non-HDL-C • LDL-C • VLDL-C • triglycerides • free fatty acids • fasting glucose • HbA1c • fasting insulin 	For analysis from Week -12 at Week 0, change from baseline to postbaseline values at each scheduled visit will be summarized. Within-treatment difference will be assessed by a Wilcoxon signed-rank test. For analysis from Week -12 at 72 weeks, the MMRM model in Section 4.3.2.2 for parameters with repeated measurements will be used. An ANCOVA model for parameters with only 1 postbaseline measurement will be used.

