- Conduct the logistic regression model on the subgroup only with terms of treatment group, country/pooled country, and sex as fixed effects and baseline body weight as a covariate. Missing body weight measurements at 72 weeks will be imputed using the imputation method described in Section 4.3.2.3, then the continuous measurements will be dichotomized into status of achieving at least 5% body weight reduction (Yes or No).
- Full logistic regression model - Treatment group, subgroup, treatment-by-subgroup-interaction, country/pooled country, and sex as fixed effects and baseline body weight as a covariate. Missing body weight measurement at 72 weeks will be imputed using the imputation method described in Section 4.3.2.3, then the continuous measurements will be dichotomized into status of achieving at least 5% body weight reduction (Yes or No).

Efficacy Estimand

- Conduct the logistic regression model on the subgroup with terms of treatment group, country/pooled country, and sex as fixed effects and baseline body weight as covariate. Missing body weight measurement at 72 weeks will be imputed by the predicted value from the MMRM model on the subgroup aforementioned, then the continuous measurements will be dichotomized into status of achieving at least 5% body weight reduction (Yes or No).

- Conduct the logistic regression model with terms of treatment group, subgroup, treatment-by-subgroup-interaction, country/pooled country, and sex as fixed effects and baseline body weight as a covariate. Missing body weight measurement at 72 weeks will be imputed by the predicted value from the full MMRM model aforementioned, then the continuous measurements will be dichotomized into status of achieving at least 5% body weight reduction (Yes or No).

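### Efficacy estimand: filling missing Week 72 responder status from a single MMRM prediction distorts responder rates and the odds ratio and understates its uncertainty

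*SAP*

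**What the plan says.** SAP Section 4.3.2.2 fits a logistic regression for ≥5% weight reduction under the efficacy estimand, "with the missing value imputed using the predicted value from MMRM analysis followed by dichotomization", and reports an odds ratio with a 95% CI. It mentions no residual draw, no repeated imputation and no variance correction. It does not say whether the prediction uses the participant's own earlier weights or only the fixed effects.

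The treatment regimen estimand is handled differently. Section 4.3.2.1 specifies "statistical inference over multiple imputation of missing data" for the ANCOVA, and its logistic model uses the same hybrid imputation. Sections 4.3.2.3 and 4.3.2.4 restrict themselves to that estimand. Section 4.1 points all type-1-error-controlled endpoints to 4.3.2.3, but that section's own scope and the specific rule in 4.3.2.2 mean the pointer does not override the single fill.

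The rule is reused in three places:

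- Table GPHM.4.2, for the binary key secondaries: "Logistic model in Section 4.3.2.1 for treatment regimen estimand and logistic model in Section 4.3.2.2 for efficacy estimand".
- Table GPHM.4.4, for the exploratory thresholds: "Logistic model in Section 4.3.2.2".
- Section 4.7.2.1, for the subgroups: "Missing body weight measurement at 72 weeks will be imputed by the predicted value from the full MMRM model aforementioned".

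The result has formal standing. Section 1.1.2.1 defines this estimand's binary summary as the "difference in response percentage between treatment conditions as assessed by odds ratio", and Section 2.1 states: "Both efficacy estimand and treatment regimen estimand will be used to assess those objectives".

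**The concern.** An MMRM handles missing data well for a mean. A responder rate is different, because the probability that a weight change falls below −5% is not the same as whether its expected value falls below −5%. Suppose a participant is predicted at −4% with a residual SD of 6 points (an illustrative assumption). The chance of response is Φ((−5+4)/6) = Φ(−0.167) = 43%, but the fill records 0%. At a predicted −6% the chance is 57%, and the fill records 100%.

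Two errors follow. Filled rates move away from the true rates, commonly towards 0% or 100%. The logistic model then counts filled statuses as if they had been measured, so the standard error is too small. That filled values are treated as observed is inferred from the absence of any variance rule in 4.3.2.2; the SAP does not say so in words.

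At stake are the efficacy-estimand responder rates, odds ratios and intervals. SAP Sections 4.3 and 4.4.1 allow other regulators and publications to rely on them.

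**Working it through.** **1. Inputs from the documents** (SAP Section 5, Protocol Section 9.2): 300 per arm; 20% and 46% achieving ≥5%; SD 10 points; 25% dropout; two-sided 0.05. Here 25% also stands in for the share without an on-treatment Week 72 weight. The documents give no visit correlations and no dropout timing or mechanism, so these are assumed and varied.

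**2. The plan's own figure.** With n = 300 × 0.75 = 225 per arm and pooled rate 0.33:

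power = Φ{[0.26 − 1.96·√(2·0.33·0.67/225)] / √[(0.20·0.80 + 0.46·0.54)/225]} = Φ(4.06) > 99.99%.

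This agrees with the stated >90%. The true unadjusted odds ratio is (0.46/0.54)/(0.20/0.80) = 3.41.

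**3. Hand check of the bias.** Under normality with SD 10, 20% responders implies a placebo mean of +3.42 and 46% a tirzepatide mean of −4.00. Let r be the correlation between the prediction and the true Week 72 value. Predictions then have SD 10r, and the share filled as responders is Φ((−5 − mean)/(10r)). With dropout independent of weight, the overall rate is 0.75 × true rate + 0.25 × filled rate.

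| Assumed r | Placebo filled → overall | Tirzepatide filled → overall | Odds ratio |
|---|---|---|---|
| 0.9 | 17.5% → 19.4% | 45.6% → 45.9% | 3.53 |
| 0.7 | 11.5% → 17.9% | 44.3% → 45.6% | 3.85 |
| 0.5 | 4.6% → 16.2% | 42.0% → 45.0% | 4.25 |

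**4. Simulation, 25% dropout per arm.** Ten scheduled weights were simulated, with prediction from the participant's own weights. Assumptions: normal data; SD growing with the square root of time; correlation 0.95, 0.90 or 0.80 per 12 weeks, or Brownian type; five countries; 65% women; covariates explaining 10% of variance. Moderate and strong missing at random (MAR) multiply the dropout odds at each visit by 2 and 4 per 10 points less weight loss at the last visit. There were 1000 trials per scenario. Ranges span the correlations and timings.

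| Dropout | Unadjusted OR (true 3.4) | Coverage | Planned adjusted OR (complete data 3.7–3.8) | Coverage |
|---|---|---|---|---|
| Independent of weight | 3.7–4.2 | 93% down to 77% | 4.1–4.9 | 91% down to 70% |
| Moderate MAR | 3.6–3.9 | 94% down to 86% | 4.0–4.5 | 92% down to 80% |
| Strong MAR | 3.5–3.7 | 94% down to 91% | 3.9–4.2 | 92% down to 87% |

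Complete-data coverage was 93–97%. The placebo ≥5% rate fell from 20% to 16–19%. In the tirzepatide arm, ≥10% fell from 27% to 23–26%, ≥15% from 13.6% to 11–13%, and ≥20% from 5.5% to 4–5%. The model SE was 3–17% below the actual spread of the estimate.

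**5. Varying the assumptions** (unadjusted ORs in the first two items).

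- 10% dropout: OR 3.5–3.7, coverage 93–95%.
- Unequal MAR dropout, 30%/20% either way: OR 3.4–4.3, coverage 95% down to 78%.
- Reversal, needing strong MAR, constant SD over visits and no covariate effect: OR 3.3 with equal dropout; 3.0–3.2 with 30% tirzepatide and 20% placebo; 2.7–3.1 (coverage 88% down to 71%) with 35% and 15%.
- Fixed-effects-only prediction, independent dropout: OR 3.1–4.6, coverage 67–87%. The 3.1 comes from runs without covariates, which the planned model does include.
- Sensitivity case only: a 12-point difference with SD 10 and 20% placebo implies 64% tirzepatide responders under normality. The OR of 7.1 becomes 7.9–10.4, with coverage 92% down to 53%.

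**6. Multiple imputation** (10 proper draws, adjusted model, 500 trials per scenario): OR 3.7–3.8 and coverage 96–98% under all three mechanisms.

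**The case against.** The strongest reply concerns scale. Against multiple imputation, the single fill's log-odds SE is only about 3–7% smaller. Much of the lost coverage comes from displacement of the odds ratio, and on the odds-ratio scale an inflated estimate can carry an interval that looks wide. In absolute terms the distortion is modest: in one set of unadjusted runs the tirzepatide ≥5% rate was 44–46% against 46%, and the risk difference was 26.6–28.2 points against 26. At 10% dropout, coverage is essentially nominal. The sizes depend on correlations and dropout patterns that the documents do not give, and 25% is a planning dropout rate rather than an estimate of missing on-treatment weights.

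All of that stands and limits the size. It does not rescue the rule. The odds ratio, not the risk difference, is the stated summary, and the log-odds SE remains too small.

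It can also be said that no decision changes, and none is shown to. Superiority at ≥5% held in at least 99.7% of runs in every 20%/46% scenario. Co-primary type I error is protected because success on both measures "needs to be achieved at the same time, no multiplicity adjustment is planned for these 2 tests", and the mean test does not use filled values. Section 1.1.2.1 assigns primary disclosure and the FDA submission to the treatment regimen estimand. This makes the problem one of estimation and precision, not of the superiority claim.

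Finally, Protocol Section 9.4.3.1 planned a longitudinal logistic regression, which would also avoid the fill. It was not tested here. Protocol Section 9.4.1 allows the SAP to substitute another method, but SAP Section 4.9 does not record the substitution.

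**Conclusion.** The concern holds; the rule should be changed. Followed as written, 4.3.2.2 gives distorted responder rates, an odds ratio that is usually too high, and an interval too narrow on the log-odds scale. At the plan's rates with 25% dropout in each arm, the planned adjusted odds ratio is about 3.9–4.9 instead of 3.7–3.8, with coverage between 92% and 70%.

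Confidence is high in the mechanism and lower in the size, which rests on the assumed correlations, dropout pattern, normality and covariate strength. The direction is not fixed: it depends on who drops out and on which prediction is used, and it reversed under strong MAR with the special assumptions above. The failure to define the prediction is a fault in itself, since two programmers could follow the text and report different odds ratios. The effect on ≥80% maintenance cannot be sized, because the documents give no distribution of lead-in weight loss.

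**What to change.** In SAP Section 4.3.2.2, replace the single predicted value with text such as:

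> Missing Week 72 weight will be multiply imputed under missing at random, separately within each treatment arm, from on-treatment (EAS) weights at scheduled visits, baseline weight, country and sex. Each completed dataset will be dichotomised and the logistic model fitted, and the log odds ratios will be combined by Rubin's rules.

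State the number of imputations and how intermittent gaps are handled. Apply the rule in Table GPHM.4.2, Table GPHM.4.4 and Section 4.7.2.1. Two minor edits would help: limit the pointer in Section 4.1 to the treatment regimen estimand, and record in Section 4.9 that the protocol's longitudinal logistic regression was replaced.

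The cost is SAP wording and one imputation model, separate from the planned retrieved-dropout and placebo-based imputations. It targets the same hypothetical estimand and needs no new data. With 25% dropout in each arm, the ≥5% odds ratio will probably be somewhat less favourable to tirzepatide and its interval wider.

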4.3.2.3. Methods for Hybrid Imputations

For efficacy analyses relative to the treatment regimen estimand, the ICEs and the resulting missing values will be handled as follows:

- **Category 1** - For missing data solely due to exceptional circumstances, such as pandemic or natural disasters (after other reasons for missing data are ruled out), missing data are considered as missing at random. The missing data will be imputed using all non-missing data of the primary outcome measurement from the same treatment arm.
- **Category 2** - For missing data due to all other ICEs, missing data will be imputed based on retrieved dropouts in the same treatment arm, defined as observed primary outcome measurements, from participants in the same treatment group who had their efficacy assessed after ED of study drug. In cases where there are not enough retrieved dropouts to provide a reliable imputation model (for example, the model implemented by the statistical analysis software [SAS] program does not converge), an alternative multiple imputation method referencing the placebo group (that is, placebo multiple imputation) will be used.

In cases where placebo multiple imputation method is used for missing data imputation in Category 2 due to not enough retrieved dropouts, the missing data in Category 1 will be imputed using all nonmissing data of the primary outcome measurement from the placebo group.

